5.3.1. Dosage Form(s) and Packaging

PF-06952229 will be provided as tablets for oral administration. The 5 mg, 25 mg, and 125 mg tablets will be supplied in separate bottles and labeled according to local regulatory requirements.

5.3.1.1. Enzalutamide

Enzalutamide will be provided by Pfizer as capsules for oral administration. The enzalutamide 40 mg capsules will be supplied in bottles and labeled according to local regulatory requirements.

5.3.2. Preparation and Dispensing

The study treatment should be dispensed at each visit per the schedule of treatment. A qualified staff member will dispense the investigational product in the bottles provided, in quantities appropriate for the study visit schedule. The patient/caregiver should be instructed to maintain the product in the bottle provided throughout the course of dosing, keep the investigational product away from children, and return the bottle to the site at the next study visit.

Only qualified personnel who are familiar with procedures that minimize undue exposure to themselves and to the environment should undertake the preparation, handling, and safe disposal of all investigational agents or drugs used in this study, including but not limited to: PF-06952229 and enzalutamide.

Dose adjustments or discontinuations should be managed according to the Section 5.4.4 below. However, per the investigator's discretion, other dose adjustments may be discussed with the sponsor.

Any unused product or waste material should be disposed of in accordance with local requirements.

5.4. Administration

5.4.1. PF-06952229

Patients will swallow the investigational product whole, and will not manipulate or chew the investigational product prior to swallowing.

PF-06952229 will be administered twice a day (BID) on an intermittent basis (7 days on/7 days off). A cycle is defined as 28 days, regardless of missed doses or dose delays.

PF-06952229 will be administered orally on an empty stomach without adjustment for body size at every cycle, CCI

No food or liquids other than water will be consumed for 2 hours before and 1 hour following each dose throughout the study.

Patients should be instructed to take their medication at approximately the same time each day (approximately every 12 hours) and to not take more than the prescribed dose at any time.

On days of scheduled clinic visits (see the Schedule of Activities for Parts 1 and 2), morning (AM) dosing of PF-06952229 should be undertaken in the clinic (ie, not at home). On those days where the morning dose of PF-06952229 is held due to a specific study visit, the second BID dosing should be taken no sooner than 8 hours, and no later than 16 hours post the first BID dosing (allowable treatment window ±4 hours). On Day 1 of Cycle 1 and Cycle 2 in Part 1B and Part 2B, only a single dose of PF-06952229 to be given to evaluate PF-06952229 PK sampling up to 24 hr time point (ie, pre-dose on Day 2 of Cycle 1 and Cycle 2).

If a patient misses a dose by more than 4 hours, he/she must be instructed not to "make it up" but to resume the subsequent dose as prescribed.

If a patient vomits 1 hour or more after taking a dose, he/she must be instructed not to "make it up" but to resume subsequent doses and site should discuss dosing with sponsor.

If a patient inadvertently takes 1 extra dose during a day, the patient should not take the next dose of PF-06952229.

[figure not shown]
In Part 1B and Part 2B of the study, PF-06952229 is given in combination with enzalutamide in patients with mCRPC. After an appropriate dose of PF-06952229 is selected in the combination dose escalation cohort (Part 1B), the combination will be tested in a dose expansion cohort (Part 2B) of enzalutamide and PF-06952229.

A dosing diary will be given to the patient to support at-home dosing.

5.4.2. Food Requirements

5.4.2.1. Food Requirements CCI

Oral PF-06952229 will be administered BID with at least 8-oz (240 mL) of water on an empty stomach. No food or liquids other than water will be consumed for at least 2 hours before and 1 hour following each dose throughout the study.

5.4.3. Enzalutamide Administration

Enzalutamide capsules are to be self-administered once daily on an outpatient basis and can be taken with or without food.

Patients receiving enzalutamide should also receive a gonadotropin-releasing hormone (GnRH) analog concurrently or should have had bilateral orchiectomy.

If a patient misses a dose by more than 8 hours, he/she must be instructed not to "make it up" but to resume the subsequent dose as prescribed. If a patient vomits 1 hour or more after taking a dose, he/she must be instructed not to "make it up" but to resume subsequent doses and site should discuss dosing with sponsor.

A dosing diary will be given to the patient to support at-home dosing.

5.4.4. Recommended Dose Modifications

Dose modifications for enzalutamide due to toxicity or intolerable side effects are described in Sections 5.4.5 and Section 5.4.6.

Every effort should be made to administer PF-06952229 on the planned dose schedule (28-day cycle, 7 days on/7 days off).

In the event of significant toxicity, dosing may be delayed and/or reduced as described below. In the event of multiple toxicities, dose modifications should be based on the worst

toxicity observed. Patients are to be instructed to notify investigators at the first occurrence of any adverse symptom.

- No dose adjustments or reductions are allowed and patients are to discontinue the study treatment at any signs of medically significant cardiac toxicity.
- Patients will continue to receive the reduced dose as a result of AEs even after toxicity recovery.
- Patients who experience a second discreet DLT-equivalent toxicity will be discontinued from the study unless they are expected to continue to receive clinical benefit after discussion with the sponsor medical monitor or designee.
- Despite dose reductions or delays of PF-06952229 the patient will retain the same 28-day cycle of 7 days on and 7 days off. Note: If a treatment interruption continues beyond Day 28 of the current cycle, then the day when treatment is restarted will be counted as Day 1 of the next cycle.
- In the case where a patient is at a dose level deemed to be above a safe level (MTD determined below this dose level) discussion between the Investigator and the sponsor to determine what is in the best interest of the patient.

Dose modifications may occur in one of three ways:

- Within a cycle: dosing interruption until adequate recovery, and if required, dose reduction during a given treatment cycle;
- Between cycles: next cycle administration may be delayed due to persisting toxicity when a new cycle is due to start;
- In the next cycle: dose reduction may be required in a subsequent cycle based on toxicity experienced in the previous cycle.

5.4.5. Dosing Interruptions

Patients experiencing Grade 3 or 4 potentially PF-06952229 treatment related toxicity or intolerable Grade 2 toxicity despite supportive care should have their treatment interrupted.

Consider permanent discontinuation of study treatment for related Grade 4 AEs of any duration. An exception to this such as emesis, as well as clinically insignificant laboratory abnormalities that resolve within 3 days on optimum treatment should be discussed between the investigator and Pfizer or its delegate.

Appropriate follow-up assessments should be done until adequate recovery occurs as assessed by the investigator.

Doses may be held for up to 2 weeks until toxicity resolution. Depending on when the adverse event resolved, a treatment interruption may lead to the patient missing all subsequent planned doses within that same cycle or may even delay the initiation of the subsequent cycle.

If the adverse event that led to the treatment interruption recovers within the same cycle, then re-dosing in that cycle is allowed. Doses omitted for toxicity are not replaced within the same cycle. Patients must maintain their original dosing schedule regardless of dose reductions or holds. The need for a dose reduction at the time of treatment resumption should be based on dose reduction criteria, unless expressly agreed otherwise following discussion between the investigator and the sponsor. If a dose reduction is applied in the same cycle, the patient may need to return to the clinic to receive new drug supply.

In the event of a treatment interruption for reasons other than treatment-related toxicity (eg, elective surgery) lasting >4 weeks, treatment resumption will be decided in consultation with the sponsor.

For enzalutamide, if a patient experiences $a \ge Grade\ 3$ toxicity or an intolerable side effect (at the PI's discretion), withhold dosing for 1 week or until symptoms improve to $\le Grade\ 2$, then resume at the same or a reduced dose (120 mg or 80 mg). Please contact Sponsor's medical monitor for any questions.

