Serum bilirubin (Guidance for non-Gilbert's Syndrome patients. Agreement between sponsor and investigator is required for these patients).	Continue at the same dose level	Continue at the same dose level	When serum bilirubin ≥2 x ULN: Hold administration until recovery to Grade 0-1 within 2 weeks, serum bilirubin <2 xULN or baseline and reduce by 1 dose level. Discontinue dose if dose delay is more than 2 weeks.* If toxicity reoccurs despite reduction, patient may be dose reduced again by another dose level upon recovery to Grade 0-1 or baseline within 2 weeks unless the patient is in the first dose group, then only 1 dose reduction is allowed. Prompt palliative measures are strongly encouraged (eg, anti-emetics).	Patients who experience related Grade 4 non- hematologic toxicities despite optimal medical intervention should be discontinued from the study. *
Thrombocytopenia	Continue at the same dose level.	Continue at the same dose level.	Hold PF-06952229 until platelets ≥75,000/mm3. For platelet counts 10,000 – 25,000/mm³, continue monitoring every 3 days until recovery to ≥25,000/mm3 (Grade 3 or less) within 2 weeks. For platelet counts ≤10,000/mm3 monitor daily until recovery to ≥25,000/mm3 (Grade 3 or less) within 2 weeks. Reduce PF-06952229 by 1 dose level. If toxicity reoccurs despite dose reduction, patient may either be held until recovery within 2 weeks and continuation at same dose, or undergo further dose reduction by another dose	Consider Permanent discontinuation of study drugs for related Grade 4 AEs of any duration.

 Table 3.
 Dose Modifications for PF-06952229 - Related Toxicity

Toxicity	Grade 1	Grade 2	Grade 3	Grade 4
			level unless the patient is in the first dose group, then only 1 dose reduction is allowed.	
Non-hematologic	Continue at the same dose level.	Continue at the same dose level.	Withhold dose until toxicity is Grade ≤1, or has returned to baseline, within 2 weeks then resume treatment at the same dose level or reduce the dose by 1 level at the discretion of the investigator.*	Permanent discontinuation of study drugs for related Grade 4 AEs of any duration. * (Exclusion to this discontinuation for emesis, and clinically insignificant laboratory abnormalities that resolve within two days on optimum treatment, additional exclusions will require agreement between the investigator and sponsor).

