Hematologic	Continue at the same dose level.	Continue at the same dose level.	Withhold dose until toxicity is Grade ≤2, or has returned to baseline within 2 weeks, then resume treatment at the same dose level.**	Permanent discontinuation of study drugs for related Grade 4 AEs of any duration.** (Exclusion to this will require agreement between the investigator and sponsor).
Acute reductions in hemoglobin	Mild symptoms; investigate for tumor hemorrhage or other sources of bleeding.	Moderate symptoms. For acute hemoglobin reduction ≥2g/dL, hold dose and investigate for tumor hemorrhage or other sources of bleeding.	For acute unexplained G ≥3 anemia (hemoglobin <8.0 g/dL), restore blood/blood volume and investigate for tumor hemorrhage or other sources of bleeding. Consider permanent discontinuation. Continuation will require agreement with Sponsor, hemoglobin >9.0 g/dL and complete resolution of the tumor hemorrhage/ bleeding event.	For acute unexplained G ≥4 anemia, replace blood/blood volume and investigate for tumor hemorrhage or other sources of bleeding. Permanent discontinuation of study drug.

^{*}Patients may continue on trial if they are receiving clinical benefit after discussion between the investigator and sponsor.

^{**}Cycle will not be extended to cover for the missing doses.

Nausea, vomiting, or diarrhea should follow guidance for the below:

Table 4. Nausea, Vomiting, or Diarrhea, Cardiac Toxicity Dose Modification Guidance

Initial management or low-grade symptoms	Follow-up or higher-grade symptoms
Dyspepsia Consider starting or giving prescription antacids (not PPIs.	For Grade ≥2, consider dose interruption until dyspepsia back to baseline. Can restart at starting dose or dose modify (eg, 1 level) depending on the severity of symptoms and other contributing factors. Consider referral to gastroenterology for evaluation of Helicobacter pylori, possible endoscopy if Grade ≥2 symptoms persist despite appropriate therapy with antacids and dose interruption.
Diarrhea Prescribe loperamide or diphenoxylate/atropine; begin if diarrhea ≤ Grade 1.	Grade 2: interrupt PF-06952229; restart when it is Grade ≤1 at same dose or at dose reduction, depending on severity of symptoms and other contributing factors.

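### Section 5.4.5 and Table 3 set different defaults after a related Grade 4 event, and for acute unexplained Grade 4 anemia the protocol both forbids and permits re-dosing

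*Protocol*

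**What the plan says.** Protocol 5.4.5 gives a general rule for related Grade 4 AEs: "Consider permanent discontinuation of study treatment for related Grade 4 AEs of any duration". Exceptions, such as emesis and "clinically insignificant laboratory abnormalities that resolve within 3 days on optimum treatment", "should be discussed between the investigator and Pfizer or its delegate".

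Table 3, which sits in 5.4.7, has five Grade 4 cells:

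- **Serum bilirubin:** patients with related Grade 4 non-hematologic toxicity "despite optimal medical intervention should be discontinued from the study".
- **Thrombocytopenia:** "Consider Permanent discontinuation of study drugs for related Grade 4 AEs of any duration".
- **Non-hematologic:** "Permanent discontinuation of study drugs for related Grade 4 AEs of any duration". Emesis and "clinically insignificant laboratory abnormalities that resolve within two days on optimum treatment" are excluded, and "additional exclusions will require agreement between the investigator and sponsor".
- **Hematologic:** the same permanent stop, with any exclusion needing investigator and sponsor agreement.
- **Acute reductions in hemoglobin:** for acute unexplained Grade 4 anemia, transfuse, look for bleeding, and stop study drug permanently. There is no footnote and no exclusion. The Grade 3 cell beside it does allow continuation, with sponsor agreement and a hemoglobin threshold.

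A footnote to the bilirubin and non-hematologic rows lets a patient who is benefiting stay on after investigator and sponsor discuss it.

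The body text of 5.4.7 separately lets a patient with a first-cycle DLT restart at the next lower dose after recovery, if investigator and sponsor judge that the patient is benefiting. It excludes no type of DLT. Section 3.2 makes treatment-related Grade 4 anemia a DLT.

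**The concern.** A site facing a related Grade 4 event finds one instruction in 5.4.5 and, usually, a firmer one in Table 3. Nothing says which governs. In most rows this changes only the starting position of a conversation with the sponsor.

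Acute unexplained Grade 4 anemia is different, because one text forbids what others permit. It is also the row closest to the known hazard of this drug. Two Grade 3 hemorrhages, one hepatic and one intracranial, led to a partial clinical hold in July 2019 (Appendix 10). The row acts while bleeding is suspected but not yet shown. A stop rule at that moment should have one reading.

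**Working it through.** The plan gives no figure on this point, so the check is mainly a comparison of texts.

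**Step 1. Strength of each Table 3 Grade 4 cell against 5.4.5.**

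| Row | Grade 4 action | Compared with 5.4.5 | Route to continue |
|---|---|---|---|
| Serum bilirubin | should come off, if toxicity persists on optimal treatment | stronger | footnote, sponsor discussion |
| Thrombocytopenia | consider stopping | same | not needed |
| Non-hematologic | permanent stop | stronger | footnote, listed exclusions, or agreement |
| Hematologic | permanent stop | stronger | agreement |
| Acute reductions in hemoglobin | permanent stop | stronger | none |

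Stronger cells: 3 permanent stops + 1 bilirubin cell = 4 of 5. Of those 4, 3 have a route through the sponsor and 1 has none.

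**Step 2. The laboratory exception.** The window is 3 days with sponsor discussion in 5.4.5, and two days outright in the non-hematologic row. A value that resolves on day 3 reaches the sponsor under both texts. Only values resolving within two days are handled differently, and the difference is whether the sponsor is consulted.

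**Step 3. Acute unexplained Grade 4 anemia, related to study drug.**

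- *Acute-hemoglobin row, any cycle:* permanent stop, no exception.
- *Hematologic row, any cycle:* the same event fits this row too, and here investigator and sponsor may agree an exclusion.
- *DLT-resumption sentence in 5.4.7, Cycle 1:* the event is a DLT under 3.2, which sets aside only events with a clear alternative explanation. The patient may therefore restart one dose level down if investigator and sponsor see benefit.
- *5.4.8:* ends participation for related Grade 3 or 4 bleeding events. Anemia with no source found is not yet such an event.
- *5.4.4:* the instruction to follow the worst toxicity addresses several toxicities in one patient, not one toxicity that fits two rows.

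The first entry forbids re-dosing, and the second and third allow it with the sponsor. No text ranks them.

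**Step 4. Another overlap in Table 3.** Grade 4 thrombocytopenia is a matter for consideration in its own row, and a permanent stop absent agreement in the hematologic row.

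**Step 5. How often.** Inputs are from Appendix 10 (Part 1A, 19 June 2020): 20 patients enrolled; two Grade 4 AEs, both judged unrelated; one related Grade 3 anemia.

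- Related Grade 4 AEs: 0/20. One-sided 95% upper limit = 1 − 0.05^(1/20) = 0.139, or 13.9%.
- Related Grade 3 anemia, one grade lower: 1/20 = 5%, Clopper-Pearson 95% interval 0.1% to 24.9%. The documents do not say whether it was acute or unexplained.

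The anemia in Step 3 is a subset of related Grade 4 AEs, and the documents give no rate for it.

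**The case against.** The strongest case against is that a sensible reader already has the answer. Table 3 belongs to 5.4.7 and has a dedicated row for this anemia. That row is specific and mandatory, while the DLT sentence is general and permissive, so the stop would ordinarily be taken to govern. Neither the DLT sentence nor the hematologic agreement clause lets a site act without the sponsor. In Cycle 1 benefit is also hard to establish: the footnotes to the Schedule of Activities place the first on-treatment scan at 8 weeks and the first on-treatment PSA at Cycle 4, while 5.4.5 allows holds of up to 2 weeks.

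Much of this stands, and it keeps the point small. A reader might infer that 5.4.7 has no rule for acute Grade 4 anemia. That is wrong: what is missing is an exception in the DLT sentence and an order of precedence between two rows. A reader might also infer that four of five cells contradict 5.4.5. Three of those four lead to the sponsor, and the bilirubin cell is conditional on optimal treatment, so for these only the default differs.

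Two parts do not stand. Sponsor involvement does not cure the anemia case, because there the sponsor could permit what the specific row prohibits. The difficulty of judging benefit early limits the Cycle 1 route only: the hematologic agreement clause requires no finding of benefit and applies in every cycle.

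**Conclusion.** The point holds in a narrow form. The default after a related Grade 4 event differs between 5.4.5 and four of the five Table 3 cells, with limited practical effect in three of them. In one case, related acute unexplained Grade 4 anemia, the protocol gives incompatible instructions on re-dosing.

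The conclusion assumes that the hematologic row covers hemoglobin, which nothing in Table 3 rules out. The event is uncommon on present data, but 20 Part 1A patients, four of them at 20 to 150 mg BID, cannot exclude a related Grade 4 rate of up to 13.9%. No patient count is projected for the anemia case.

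Two larger readings are not supported. One is that a patient with a shown drug-related Grade 3 or 4 bleed could be re-dosed: 5.4.8 stops that patient. The other is that dose finding is compromised: Grade 4 anemia counts as a DLT under 3.2 whether or not dosing later resumes, so DLT counts, MTD and sample size do not change.

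**What to change.** 1. In 5.4.5, replace the sentence on considering discontinuation, and its 3-day exception, with: *For related Grade 4 AEs, follow the Grade 4 column of Table 3, including its stated exceptions.*
2. Add to the DLT-resumption sentence in 5.4.7: *subject to the Grade 4 column of Table 3; dosing may not resume after acute unexplained Grade 4 anemia.*
3. Add under Table 3: *The acute-hemoglobin row overrides the general hematologic row.*

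Two things to avoid. A blanket rule that any specific row overrides the general one would move Grade 4 thrombocytopenia to the weaker instruction, which is the wrong direction in a study with a bleeding hold. The sponsor should state separately which row governs low platelets. Nor is a new agreement requirement needed for emesis or two-day laboratory values. Under edit 1 they keep the outright exclusion in the non-hematologic row, and the sponsor discussion now in 5.4.5 falls away for them.

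The cost is a protocol clarification and slightly less site and sponsor discretion after a Grade 4 event. No procedures or patients are added.

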5.4.6. Dose Delays

Re-treatment following treatment interruption for PF-06952229 treatment-related toxicity or at the start of any new cycle may not occur until all of the following parameters have been met:

- ANC $\ge 1,000 / \text{mm}^3$;
- Platelets count $\geq 50,000/\text{mm}^3$;
- Non-hematologic toxicities have returned to baseline or Grade ≤1 severity (or at the investigator's discretion, Grade ≤2 if not considered a safety risk for the patient).

If a treatment delay results from worsening of hematologic or biochemical parameters, the frequency of relevant blood tests should be increased as clinically indicated.

If these conditions are met within 4 weeks of treatment interruption, PF-06952229 may be resumed. Refer to the Dose Reductions section for AEs that require dose reduction at the time of treatment resumption.

If these conditions are not met, treatment resumption must be delayed for up to a maximum of an additional 2 weeks. If patients require discontinuation of PF-06952229 for more than 6 weeks at any time during the study, then study treatment should be permanently discontinued unless the investigator's benefit/risk assessment suggests otherwise after discussion with the sponsor's medical monitor or designee.

If a treatment interruption continues beyond Day 14 of the current cycle, then the day when treatment is restarted will be counted as Day 1 of the next cycle.

If patients require discontinuation of study drug for more than 4 weeks at any time during the study, then study treatment should be permanently discontinued, unless the investigator's benefit/risk assessment suggests otherwise and after discussion with the sponsor's medical monitor.

For enzalutamide, if a patient experiences $a \ge Grade\ 3$ toxicity or an intolerable side effect (at the PI's discretion), withhold dosing for 1 week or until symptoms improve to $\le Grade\ 2$, then resume at the same or a reduced dose (120 mg or 80 mg). Please contact Sponsor's medical monitor for any questions.

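### For related Grade 3 non-hematologic toxicities with no rule of their own, Protocol 5.4.6 lets the investigator alone restart PF-06952229 at residual Grade 2, Table 3 requires Grade ≤1 or baseline, and no text says which governs

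*Protocol*

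**What the plan says.** Protocol 5.4.5 sends patients with potentially related Grade 3 or 4 toxicity into a treatment interruption. Protocol 5.4.6 then governs re-treatment after any interruption for PF-06952229-related toxicity, and also the start of any new cycle. Its non-hematologic condition is baseline or Grade ≤1, "or at the investigator's discretion, Grade ≤2 if not considered a safety risk for the patient". It continues: "If these conditions are met within 4 weeks of treatment interruption, PF-06952229 may be resumed." If the conditions are not met, "treatment resumption must be delayed for up to a maximum of an additional 2 weeks".

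Table 3 in 5.4.7 treats the two kinds of Grade 3 event differently:

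- Non-hematologic: "Withhold dose until toxicity is Grade ≤1, or has returned to baseline, within 2 weeks". Investigator discretion here covers only whether to resume at the same dose or one level lower.
- Hematologic: "Withhold dose until toxicity is Grade ≤2, or has returned to baseline within 2 weeks".

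The non-hematologic cell carries the asterisk footnote: "Patients may continue on trial if they are receiving clinical benefit after discussion between the investigator and sponsor."

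The only pointer from 5.4.6 to 5.4.7 is about dose level: "Refer to the Dose Reductions section for AEs that require dose reduction at the time of treatment resumption." It does not mention the recovery grade.

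**The concern.** The default in 5.4.6 agrees with Table 3. The difficulty is the added discretion. It extends to a patient recovering from a related Grade 3 non-hematologic event, and it needs only the investigator's own judgment that Grade 2 is not a safety risk. Table 3 keeps that patient off drug unless the sponsor has been consulted.

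At stake are re-dosing safety and consistency between sites in a first-in-patient study that has already been under a partial clinical hold (Protocol 1.5). Whether such a patient restarts should not depend on which section the site opens, and a site looking for a restart criterion could reasonably stop at the section on dose delays.

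**Working it through.** No statistical figure is involved, so the check sets the rules side by side.

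| Feature | 5.4.6 | Table 3, Grade 3 non-hematologic |
|---|---|---|
| Events covered | Any related interruption; any new cycle | Related Grade 3 non-hematologic |
| Recovery grade | ≤1 or baseline; ≤2 at discretion | ≤1 or baseline |
| Who may relax the grade | Investigator alone | Only after sponsor discussion, with clinical benefit (footnote) |
| Time stated | 4 weeks, then up to 2 more | 2 weeks |
| Consequence after that time | Discontinuation unless discussed with the sponsor | None stated |

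**Step 1: a case where the rules part.** A related Grade 3 non-hematologic event falls to Grade 2 on day 10. Under 5.4.6 the investigator may restart. Under Table 3 the drug is still withheld.

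**Step 2: which reading fits the rest of 5.4.7.** Table 3 accepts Grade ≤2 after a Grade 3 hematologic event but not after a non-hematologic one, so the difference looks deliberate. The body of 5.4.7 requires Grade ≤1 or baseline even after recurrent, intolerable Grade 2 toxicity. Its sentence on related Grade 3 events sets a similar limit (it reads Grade <1 in the available text, perhaps a conversion slip for ≤1). The 5.4.6 discretion is therefore looser after Grade 3 than 5.4.7 is after Grade 2.

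**Step 3: who is exposed.** Remove events with their own rule:

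- first-cycle DLTs: the note in 3.2 requires Grade 0-1 or baseline, a reduced dose and sponsor discussion
- cardiac toxicity: discontinuation (1.5.2.1, 5.4.4, Table 4)
- related Grade 3 or 4 bleeding: discontinuation (5.4.8)
- bilirubin: its own row in Table 3
- QTcF: 7.1.5

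What remains is other related Grade 3 non-hematologic toxicity, mainly after Cycle 1 and in Part 2. Appendix 10 gives a partial view at June 2020: 25 Grade 3 events, of which 3 were attributed to the drug, 21 were unrelated and 1 had no causality reported (3 + 21 + 1 = 25). The 3 attributed events were anemia and two hemorrhages, so none falls in the exposed group. The event without causality was fatigue, which would fall in it if related.

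**Step 4: hold time.** In days: 2 weeks = 14 (5.4.5, 5.4.7, Table 3); 4 weeks = 28 (5.4.6, 5.4.7); 4 + 2 weeks = 42 (5.4.6). Ratios are 28/14 = 2 and 42/14 = 3. Within Table 3 only the bilirubin row says what follows after 2 weeks: "Discontinue dose if dose delay is more than 2 weeks". The 28- and 42-day limits also conflict inside 5.4.6, where one paragraph sets discontinuation at more than 6 weeks and a later one at more than 4 weeks, each with an exception after sponsor discussion.

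**The case against.** The strongest answer is that the rules are compatible. 5.4.6 is framed as a minimum, since re-treatment is barred until its conditions are met, and Table 3 adds a stricter, toxicity-specific hold. A site that follows Table 3 satisfies both. Platelets follow the same pattern: at least 50,000/mm³ in 5.4.6, but at least 75,000/mm³ after Grade 3 thrombocytopenia in Table 3. The discretion also has a natural use at the start of a new cycle, because Table 3 continues dosing through Grade 2 non-hematologic toxicity.

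This reading is plausible and may be what was intended. But no sentence states it. 5.4.6 also gives positive permission to resume, and 5.4.5 leaves adequate recovery to the investigator's assessment. The objection shows that compliance with both rules is possible. It does not show that a site relying on 5.4.6 would know it must look further.

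Three stronger readings are tempting but not supported:

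- A reader might infer that any patient with a related Grade 3 event can be re-dosed without the sponsor. The event-specific rules in Step 3 rule that out.
- A reader might treat the 2-week and the 4- or 6-week limits as an equal conflict. The Table 3 non-hematologic cell attaches no consequence to passing 2 weeks, and the 3.2 note sits directly under the criterion that makes a delay of more than 2 weeks a DLT, yet allows continuation after recovery.
- A reader might count the other restart rules set at Grade ≤1 and call 5.4.6 the lone outlier. Several of those concern Grade 2 events (recurrent intolerable Grade 2, diarrhea, nausea), the dyspepsia entry only suggests an interruption, and one 5.4.7 sentence on DLTs names no grade.

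**Conclusion.** The point holds as a conflict between two stated safety rules on recovery grade: ≤2 on the investigator's judgment against ≤1 or baseline, with sponsor discussion for any exception. It is limited to related Grade 3 non-hematologic toxicity with no event-specific rule. The hold-time differences are real but secondary.

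The number of patients affected cannot be estimated, because the documents give no recovery grades or hold durations. A reader might infer biased dose finding; the documents do not support that. First-cycle DLTs are classified under 3.2 and SAP 9.1 independently of the 5.4.6 discretion, and no effect on the MTD or any analysis is claimed. The conclusion assumes only that a site may act on 5.4.6 as written. The point is worth correcting in the next amendment.

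**What to change.** Add to 5.4.6:

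> The Grade ≤2 discretion does not apply after a related Grade 3 non-hematologic toxicity. The recovery grade in Table 3 (Grade ≤1 or baseline) applies, and any exception needs the sponsor discussion in the Table 3 footnote. This does not change the discontinuation rules for cardiac toxicity and related Grade 3 or 4 bleeding (1.5.2.1, 5.4.4, 5.4.8), the rules after a DLT (3.2, 5.4.7), the bilirubin row, the QTcF rule (7.1.5), or any dose reduction required by 5.4.7.

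The last sentence is needed because a bare statement that Table 3 governs could be read as a restart route for events that must lead to discontinuation, or as favouring its same-dose option over a required reduction.

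Also state in 5.4.6 that a hold longer than 2 weeks after such an event needs sponsor discussion before restart, and keep one outer limit of 4 weeks, as in 5.4.7, in place of the conflicting 4- and 6-week limits. The discretion stays available for Grade 2 toxicity present at the start of a new cycle.

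The cost is a few sentences in an amendment, with no new data collection and no change to the DLT definition in 3.2 or SAP 9.1. The clinical downside is longer holds, and possibly discontinuation, for some patients with persistent Grade 2 toxicity unless the sponsor agrees to continue.
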